6.4.4 Patient completion or early withdrawal

Subjects who receive the Treatment procedure complete the study 36 months after the initial implant procedure or when they choose to withdraw from the study, if earlier than 36 months post-procedure. In the event of a continuing SAE related to the Coil system, the subject will be asked to return for follow-up until the SAE has resolved or is deemed to be continuing indefinitely. Control subjects who do not crossover to treatment will exit the study immediately.

6.4.5 Data Collection

Informed consent, baseline assessments, procedure data, adverse event data, medications, and effectiveness measures will be collected and entered into the EDC system. The eCRFs will be completed by the PI (or an authorized member of the investigator's staff) at the participating site and entered into the EDC database. All entries into the EDC system will be in English.

PIs will be provided a process for assigning a de-identified number to the Subject and will be asked to keep any study paperwork in a secure private area. Electronic audits will be in place to help ensure that data entered is within reasonable limits. This also allows the site to be queried regarding inappropriate data. The study will also be monitored by Boston Scientific Corporation and/or their designees for the duration of the study to ensure accurate collection of data and compliance.

6.5 Trial Evaluations and Procedures

6.5.1 Informed Consent Process

All Subjects must sign an ICF approved by the relevant IEC to be enrolled in the study.

The PI or delegate will review the treatment plans with the Subject, and the Subject will have an opportunity ask questions about trial procedures, the required visit schedule, risks and benefits of the study treatments, and alternative treatment options prior to signature. The Subject will receive a copy of the signed ICF to keep for their records.

Subjects will be informed of any revisions of the ICF and any revisions must be signed and kept in the Subject study file.

Acquisition of the informed consent or any revisions should be documented in the Subject's medical record and the ICF signed and dated by the individual who conducted the informed consent discussion.

6.5.2 Demographics

The following demographic data will be obtained: date of birth, gender, race, ethnicity, weight and height.

6.5.3 Medical History

Medical history, including existing comorbidities deemed clinically significant (e.g., respiratory, pulmonary, cardiovascular, renal, liver, cerebral vascular, vascular, and psychiatric conditions and diseases) will be collected by the investigator.

Diagnosis and medical history for emphysema will be recorded separately, and will include at minimum the number of years since the subject was diagnosed with emphysema, characteristics of the emphysema, treatment history, and history of hospitalization events due to emphysema.

Smoking status and physical activity will be captured.

6.5.4 Vital Signs, Blood panel and Echocardiogram

Assessments of blood panel at baseline will follow routine standards (Haemoglobin, Hematocrit (HCT), White Blood Cells, Platelet count, Prothrombin time, Eosinophil leucocytes, INR, Sodium, Potassium, Chloride,

Glucose, Total Protein, Albumin, Blood Urea Nitrogen, Creatinine, Cardiac panel including BNP-test and other biomarker if available).

Assessment of pulmonary hypertension and left ventricular ejection fraction will be performed at baseline and

documented in the CRF.

Pregnancy test need to be performed for females of child-bearing potential prior to radiographic procedures at baseline and implant procedures.

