16. Severe pulmonary hypertension (Right Ventricular Systolic Pressure (RVSP) > 50 mm Hg (preferably measured by right heart catheterization) or other signs of Pulmonary Hypertension (PHT) with right ventricular dysfunction)
17. Severe hypercapnia ($\text{PaCO}_2 > 55$ mmHg on room air) and/or severe hypoxemia ($\text{PaO}_2 < 45$ mm Hg on room air, High altitude criterion: $\text{PaO}_2 < 30$ mm Hg)
18. Previous Lung Volume Reduction (LVR) surgery, lung transplantation, lobectomy, LVR devices or other device to treat COPD in either lung.
19. Diagnosed with alpha-1 antitrypsin deficiency
20. Diffusion Capacity of the Lungs for Carbon Monoxide (DLCO) < 20 %
21. Significant, recent or unstable cardiac disease defined as severe heart failure (Left Ventricular Ejection Fraction (LVEF) < 45% despite optimal medical management), unstable cardiac arrhythmia or coronary artery disease (angina on activity), or ischemic event in the past 6 months
22. Body Mass Index (BMI) > 30.
23. Participation in any other clinical study.
24. Subject is pregnant or lactating, or plan to become pregnant within the study timeframe.
25. If treated in France, Subject is a “personne vulnérable” as defined by French regulation.

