4.3 Subject Crossover

Control group Subjects will be eligible for crossover to Treatment as soon as possible. Control subjects will be eligible for crossover if they still meet all inclusion and exclusion criteria, and if the patient is deemed to benefit from the Coil treatment by the investigator, based on best medical judgment. Crossover subjects will continue in the study through 36 months from first Coil implant. If Control subjects do not crossover to treatment, they will exit the study immediately.

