5.1.2 Implant Procedure

The Coil is delivered through a standard 2.8 mm Inner Diameter therapeutic bronchoscope. The Coil System is a two-part system that consists of:

- 1) Sterile implants (3 sizes: 100 mm, 125 mm, and 150 mm)
- 2) Sterile, disposable, single-use (single-patient) Delivery System consisting of a Cartridge, a Catheter, a Guidewire and Forceps.

Each Coil implantation procedure must be performed under fluoroscopy in accordance with the IFU. Use of general anesthesia or conscious sedation is at the discretion of the bronchoscopist and anesthesiologist. A complete treatment includes two treatments: the first side (upper or lower lobe Coil implantation) followed by treatment of the contralateral side. Procedures must be staggered (contralateral procedure should be scheduled approximately 2 months after first treatment), such that both lungs are not treated during a single procedure. Lobar targeting for Coil implantation will be based on quantitative CT (QCT) densitometry analysis provided by PneumRx, per the PneumRx QCT Service.

The Treatment is considered complete after the contralateral procedure. The investigator can decide to limit the Treatment to one side if there are contraindications preventing the Treatment of the contralateral side.

Each center's PI, or a primary implanter, will perform all Coil treatments in the study if possible. If necessary, a secondary implanter will be trained as a back-up if primary implanter is unavailable.

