5.1.3 Post-implant Management

Prophylactic regimen of medications should be administered according to the IFU and standard of care (SoC).

Per the IFU, a chest X-ray or still fluoroscopy image should be done post-procedure to verify Coil placement and to ensure there is no pneumothorax. A second, confirmatory chest X-ray should be done before discharge a minimum of 4 hours following the first chest X-ray. The second, confirmatory X-ray must be two views, posterior anterior (PA) and Lateral.

The Subject will be counseled on expected side-effects of the Coil procedure, including the potential AEs listed in Section 7.7. The Subject will be instructed to contact the treating physician immediately should any of the potential AEs be experienced. It is particularly important that Subjects be instructed at discharge to contact their implanting physician if they experience symptoms that may be indicative of pneumonia or CAIRS/CAO, to ensure that appropriate treatment is delivered.

Follow-up visits should be conducted per the schedule below. Study specific follow -up visits should take place during exacerbation free periods defined as 30 days with symptoms within normal day to day variability.

Treatment Group Subjects:

Visit	Visit window
Baseline visit	Eligibility, inclusion
Randomization	
First coil treatment	No more than 45 days post baseline visit
Second coil treatment	2 months +/- 4 weeks post first procedure
12-month follow-up	12 months +/- 4 weeks post first procedure
36-month follow-up	36 months +/- 4 weeks post first procedure

Control Group Subjects:

Visit	Visit window
Baseline visit	Eligibility, inclusion
Randomization	
First coil treatment	
Second coil treatment	2 months +/- 4 weeks post first procedure
12-month follow-up	12 months +/- 4 weeks post first procedure
36-month follow-up	36 months +/- 4 weeks post first procedure

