6.4.1 Baseline Visit

After the Subject provides informed consent, the Subject will be evaluated to ensure they are appropriate candidates for use of the Coil System. Eligibility to enroll in the study is assessed as described in Section 4.2.

The following evaluations will be performed as part of the Baseline visit.

- Informed Consent
- Demographic Information
- Medical history information, including comorbidities, smoking status, previous treatments of emphysema and baseline characteristics, physical activity, rehabilitation status
- Medications
- Pulmonary Function Test (PFT)
- Six Minute Walk Test (6MWT)
- Modified Medical Research Council mMRC dyspnea scale will be completed.
- QoL assessments: SGRQ, CAT, and EQ5D will be completed
- Blood gas, including CoHB for smoking cessation confirmation
- Blood test including cardiac panel with BNP test and other biomarker, if available
- Pregnancy test for females of child-bearing potential prior to radiographic procedures
- Echocardiogram
- Vital signs
- Inspiratory and expiratory HRCT (Note: a HRCT scan (inspiratory and expiratory) performed within 6 months prior to baseline may be used if it was acquired per the PneumRx QCT service protocol.)
- Chest X-Ray.

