6.4.3 Follow-Up Visits

Follow-up office visits will be conducted at 12, and 36 months post first Endobronchial Coil treatment for both Treatment group subjects and Crossover subjects..

Follow-up visits should be conducted per the schedule below. Study specific follow-up visits should take place during exacerbation free periods defined as 30 days with symptoms within normal day to day variability.

12- and 36-month study follow-up visits will include:

- PFT
- AE review
- Medications
- Inspiratory and expiratory HRCT

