6.5.14 Imaging

Chest X-rays (PA and lateral) will be performed at Baseline and post-procedure in accordance with the IFU. These will be documented in the appropriate eCRF, subject-identifying information redacted, and submitted to Boston Scientific Corporation upon request.

HRCT will be performed at the Baseline Visit and 12 and 36 month Follow-up Visits. HRCT will include both inspiratory and expiratory scans completed per the recommendations provided as part of the PneumRx QCT service.

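### No pregnancy test is scheduled before the study HRCT scans at 12 and 36 months

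*Combined protocol and SAP*

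**What the plan says.** The testing rule appears in the same words in Sections 4.2 and 6.5.4: "Pregnancy test need to be performed for females of child-bearing potential prior to radiographic procedures at baseline and implant procedures". Sections 6.4.1 and 6.4.2 list a test at the baseline and implant visits, and the Section 1 schedule marks it at Baseline, Treatment 1 and Treatment 2. These places agree with one another.

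CT imaging extends further. Section 6.5.14 states: "HRCT will be performed at the Baseline Visit and 12 and 36 month Follow-up Visits". Each scan is both inspiratory and expiratory. In Section 6.4.3 the list headed "12- and 36-month study follow-up visits will include" contains lung function, adverse event review, medications and HRCT, and the synopsis gives the same four items. Neither list contains a pregnancy test, and the schedule leaves the 12- and 36-month cells of that row blank while marking HRCT in both.

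Exclusion criterion 24 in Section 4.2.2 reads: "Subject is pregnant or lactating, or plan to become pregnant within the study timeframe". Section 4.3 applies the criteria again before a Control subject is treated: "Control subjects will be eligible for crossover if they still meet all inclusion and exclusion criteria".

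**The concern.** The rule ties the test to radiographic procedures, and the follow-up HRCT is a radiographic procedure that the protocol itself requires. A subject who follows the schedule exactly could be scanned at 12 or 36 months during an unrecognised pregnancy with no scheduled check.

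Implant visits justify a test for further reasons: fluoroscopy, sedation or anesthesia, and an implant. The baseline test, however, is worded around imaging, and the protocol gives no reason for dropping it when the same kind of scan is repeated later.

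This is a gap in coverage. The sections do not contradict one another.

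**Working it through.** **Which visits have a scan and which have a test** (Section 1 schedule, agreeing with 6.4.1 to 6.4.3 and 6.5.14)

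| Visit | HRCT | Pregnancy test |
|---|---|---|
| Baseline | yes | yes |
| Treatment 1 | no | yes |
| Treatment 2 | no | yes |
| 12 months | yes | no |
| 36 months | yes | no |

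Two of the three HRCT visits have no scheduled test.

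**Can the last scheduled test stand in?** Section 5.1.3 puts the second procedure at "2 months +/- 4 weeks post first procedure", and both follow-up visits carry a window of 4 weeks either side, counted from the first procedure. Four weeks is 28 / 30.44 = 0.92 months, so the windows in months from the first procedure are:

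- Treatment 2: 2 ± 0.92 = 1.08 to 2.92
- 12-month visit: 12 ± 0.92 = 11.08 to 12.92
- 36-month visit: 36 ± 0.92 = 35.08 to 36.92

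Section 5.1.2 also allows treatment to stop after one lung: "The investigator can decide to limit the Treatment to one side if there are contraindications preventing the Treatment of the contralateral side". In that case the last test is at Treatment 1, which is month 0. The time from the last scheduled test to each scan is then:

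| Treatment | Scan | Nominal (months) | Shortest | Longest |
|---|---|---|---|---|
| Two-sided | 12 months | 12 − 2 = 10 | 11.08 − 2.92 = 8.2 | 12.92 − 1.08 = 11.8 |
| Two-sided | 36 months | 36 − 2 = 34 | 35.08 − 2.92 = 32.2 | 36.92 − 1.08 = 35.8 |
| One-sided | 12 months | 12 | 11.1 | 12.9 |
| One-sided | 36 months | 36 | 35.1 | 36.9 |

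Even the shortest interval exceeds 8 months, so no earlier test can serve as the pre-scan test.

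**Does the exclusion criterion fill the gap?** Criterion 24 covers current and planned pregnancy, at entry and again at crossover. Both checks come before the first implant. An unplanned pregnancy that begins after treatment is outside its reach.

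**How many visits and subjects?** Inputs are 80 Treatment and 40 Control subjects (Section 8.1) and two follow-up scans per treated subject.

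- No Control subject crosses over: 80 × 2 = 160 scan visits
- All 40 cross over: (80 + 40) × 2 = 240 scan visits

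Both counts are ceilings: they take every subject as treated and followed to 36 months, and they include men and women who are not of child-bearing potential. The documents give no age or sex distribution. With an assumed share of 0% to 5%, the range is 120 × 0 = 0 to 120 × 0.05 = 6 subjects, and 240 × 0 = 0 to 240 × 0.05 = 12 tests.

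The baseline scan is left out of these counts, because Section 6.4.1 accepts an HRCT "performed within 6 months prior to baseline may be used" if it met the imaging protocol.

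**The case against.** The strongest case against the point is that it may affect nobody. Section 2.1 remarks on the advanced age of most emphysema patients, the entry criteria select severe hyperinflated disease, and criterion 19 removes diagnosed alpha-1 antitrypsin deficiency. The assumed range starts at zero, and its upper end of 5% has no source in the documents.

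Second, Section 10.10 describes the study procedures as routine follow-up or standard care, which makes local checks before imaging a relevant safeguard. The QCT service instructions and the study operations instructions may also require a test. They are not among the documents, and the consent pages were removed, so any pregnancy advice there cannot be assessed.

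Third, the present scope has a rationale. The baseline test supports criterion 24, and the implant test covers the procedure as a whole.

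Fourth, an amendment is not free. Section 10.7 requires investigator and sponsor approval and ethics submission, at up to 30 sites. Randomization is described as complete, so an amendment reaches only the visits still outstanding, and the documents do not say how many those are.

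All of this limits the size of the point, and the 160 and 240 visit counts should not be read as its size. None of it places a test before the follow-up scans. A safeguard that may exist locally is not one that the protocol requires, and a rationale for testing at baseline and implant is not a reason to omit the test before a later scan.

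**Conclusion.** The point holds. The protocol requires HRCT at 12 and 36 months and schedules no pregnancy test at either visit. The last scheduled test is at least 8.2 months old at the first of these scans and at least 32.2 months old at the second.

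The practical size is small: 0 to 6 subjects and 0 to 12 tests over the whole trial, resting on the assumed 0% to 5% share, full crossover and full follow-up. Confidence is high for what the protocol text says. It does not extend to what sites do in practice, which the documents do not show.

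This is a cheap improvement in subject safety. It has no bearing on the co-primary endpoints or on the FEV₁ summaries at 12 and 36 months in Section 8.5.

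**What to change.** - In the Section 1 schedule, mark the pregnancy test at 12 and 36 months, for women of child-bearing potential only.
- Add it to the follow-up visit lists in the synopsis and Section 6.4.3.
- Extend the sentence in Sections 4.2 and 6.5.4 so that it covers baseline, implant procedures and follow-up HRCT.
- State that after a positive test the HRCT is omitted, while lung function, adverse event review and medication review go ahead.
- In the same edit, align Section 3.2, which limits biological samples to blood drawn at screening. The tests already scheduled at implant visits fit awkwardly with that sentence.

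The cost is two marks in the schedule, one line in each of two lists, a few words in 4.2, 6.5.4 and 3.2, and at most about 12 tests of a kind already used in the trial, under the assumed share. The main burden is the approval route in Section 10.7, so the change is best combined with the next amendment made for another reason, provided follow-up scans are still outstanding by then.

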6.5.5 Pulmonary Function Test

PFT will include post bronchodilator Spirometry, Lung plethysmography, and DLCO_{sb} at Baseline and Follow- up Visits. Baseline Visit should also include pre bronchodilator spirometry to assess bronchodilator reversibility. Tests should be conducted per ATS/ERS standards and will be assessed by an independent, 3rd party vendor for adherence to these standards to ensure consistency and quality of data collection at baseline.

6.5.6 Six Minute Walk Test

6MWT will be conducted by a qualified individual according to ATS/ERS Guidelines as specified in the schedule of visits.

6.5.7 Medication and Prior Treatment History

The use of concurrent respiratory, cardiac, anticoagulant, antibiotic, and steroid medications (medications taken within 30 days of screening and during the conduct of the trial) will be recorded and entered in to the EDC.

6.5.8 Eligibility Review Committee

Data from subjects who have signed the ICF and are considered by the treating physician to be eligible to receive the Coil treatment as part of the trial, should be submitted to the ERC for final assessment of eligibility for the study. The ERC will review the data in accordance with the procedures agreed to in the ERC Charter.

The ERC will consist of a minimum of 5 interventionalists. The purpose of the ERC is to provide peer-review from interventionalists who are extremely knowledgeable in the procedure and patient selection to confirm eligibility and suitability of subjects selected for participation in the ELEVATE trial. The ERC shall provide the final decision with regard to enrollment.

Data that will be provided to the ERC for review include PFT, medical history, and HRCT with QCT data. Two (2) of the 5 ERC members will be selected via random number generation. A member may decline to evaluate a subject file; in this case another member will be randomly selected. If 2 members agree to either approve or deny enrollment, that decision will be final. If the 2 members disagree, then a third, randomly selected member will independently review the case to determine eligibility. ERC members will document the reason for denial if the subject is not deemed not eligible for the study. The process will be blinded, such that a member receiving a request for review will not know how others have voted. An ERC member cannot review his /her own subject, in which case another ERC member will be randomly selected to review the data.

The determination of study eligibility will be recorded on the relevant eCRF.

6.5.9 Expert Radiology Review

All baseline CT scans will be reviewed by expert Radiologists in accordance with the ELEVATE Radiology Review Manual. An eCRF providing a detailed pulmonary radiologic assessment will be completed by one of 3 independent radiologists for each subject. The report from the expert Radiologist will be reviewed by the ERC as part of the subject eligibility assessment.

6.5.10 Randomization/Enrollment Event

If a Subject is deemed eligible to participate in the trial, the Subject is assigned the next sequential Randomization Assignment via the study EDC. Randomization will be determined using assignment by a computer-generated

randomization scheme. Upon randomization/enrollment, each Subject will be assigned a unique numeric Subject identity code.

A total of 120 Subjects were randomized in a 2:1 ratio Treatment to Control respectively (80 Treatment group subjects, 40 Control group subjects).

6.5.11 Implant Procedure Record

Details on the Coil treatment procedures performed on study Subjects will be recorded in the relevant eCRF. Procedure data collected and entered into the EDC system will include:

- Treatment date
- Duration of bronchoscopy procedure
- Duration of fluoroscopy
- Duration of hospital stay
- Lung lobe and location treated
- Number and size of implanted Coils
- Procedural SAEs (see Section 7)
- Device malfunctions
- Prophylactic medications (antibiotics, steroids – including dosage and start/stop dates)

6.5.12 Coil Removal

Coil removal following implantation (defined as removal of a Coil after termination of the Coil implantation procedure) must be medically indicated and performed in accordance with the IFU. Each occurrence of post - procedure Coil removal will be recorded as an SAE in the appropriate eCRF. Recommendations regarding Coil removal will be provided to the study site as part of the Study Operational Instructions (SOI). To perform bronchoscopic Coil removal subsequent to the implantation procedure, you must have a therapeutic bronchoscope with a minimum 2.0mm inner diameter working channel and a 65cm maximum working length.

6.5.13 Quality of Life

QoL instruments suitable for Subjects being treated for emphysema (i.e., SGRQ, CAT, EQ5D, and mMRC) will be administered at study visits as specified in the schedule of visits.

